### Last contact date

The last contact date will be derived for patients not known to have died at the LPLV using the last complete date among the following:

**Table 2-1      Last contact date data sources**

Source data	Conditions
Date of start of study treatment	No Condition
Date of Randomization	No Condition
Last contact date/last date patient was known to be alive from Survival Follow-up page	Patient status is reported to be alive, lost to follow-up or unknown
Start/End dates from further antineoplastic therapy	Non-missing medication/procedure term
Start/End* dates from drug administration record	Non-missing dose. Doses of 0 are allowed
End of treatment date from end of treatment page	No condition
Any specific efficacy assessment date	Evaluation is marked as 'done'
Laboratory [REDACTED] PK collection dates	Sample collection marked as 'done'
Vital signs, ECG date	At least one non-missing parameter value
Performance Status date	Non-missing performance status
Start/End dates of AE	Non-missing verbatim term

The last contact date is defined as the latest complete date from the above list on or before the LPLV. The LPLV will not be used for last contact date, unless the patient was seen or contacted on that date. No date post LPLV will be used. Completely imputed dates (e.g., the analysis cut-off date programmatically imputed to replace the missing end date of a dose administration record) will not be used to derive the last contact date. Partial date imputation is allowed for event (death)/censoring is coming from 'Survival information' eCRF.

The last contact date will be used for censoring of patients in the analysis of overall survival.

## **Hematological toxicities and recovery**

Thrombocytopenia is defined as a platelet count below  $20.0 \times 10^9/L$  as reported on the eCRF Local Lab Results - Hematology.

The duration of thrombocytopenia is defined as (first date of increase of platelets over  $20.0 \times 10^9/L$  – first date of decrease of platelets below  $20.0 \times 10^9/L$  for the considered period + 1). If the patient had a platelet transfusion during the period, the patient is considered as not assessable.

The time between chemotherapy start and non-transfused recovery from thrombocytopenia is defined as (first date of increase of platelets over  $20.0 \times 10^9/L$  – date of first chemotherapy (cytarabine or daunorubicin in induction phase, or high dose cytarabine in consolidation phase) administration for the considered period + 1). If the patient had a platelet transfusion during the period, the patient is considered as not assessable.

Neutropenia is defined as an absolute neutrophil count below  $0.5 \times 10^9/L$  as reported on the eCRF Local Lab Results - Hematology.

The duration of neutropenia is defined as (first date of increase of absolute neutrophil count over  $0.5 \times 10^9/L$  – first date of decrease of absolute neutrophil count below  $0.5 \times 10^9/L$  for the considered period + 1).

The time between chemotherapy start and recovery from neutropenia is defined as (first date of increase of absolute neutrophil count over  $0.5 \times 10^9/L$  – date of first chemotherapy (cytarabine or daunorubicin in induction phase, or high dose cytarabine in consolidation phase) administration for the considered phase + 1).

Additional analyses might be performed, if need be, in order to better characterize the influence of concomedications and blood transfusions on the kinetics of hematologic recovery.

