## **Hematological toxicities and recovery**

The following summary tables will be provided by cycle during induction and consolidation:

- Number and percentage of patients having at least one thrombocytopenia, and among them the duration of thrombocytopenia and the time between chemotherapy (cytarabine or daunorubicin) start and non-transfused recovery from thrombocytopenia (see definitions in

[Section 2.1.1](#)).

- Number and percentage of patients having at least one neutropenia, and among them the duration of neutropenia and the time between chemotherapy (cytarabine or daunorubicin) start and recovery from neutropenia (see definitions in [Section 2.1.1](#)).
- Number and percentage of patients requiring platelet transfusion.
- Number and percentage of patients requiring red blood cell transfusion.

All blood component transfusion data will be listed.

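### Thrombocytopenia duration and recovery are summarised only in patients never given platelets in the period, a subset selected by the outcome, with no rule for patients who do not recover

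*SAP*

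**What the plan says.** The definitions are in SAP 2.1.1, under hematological toxicities and recovery. "Thrombocytopenia is defined as a platelet count below" 20.0 x 10^9/L. Duration runs from the first fall below that level to the first rise above it. Time to recovery runs from the first chemotherapy dose to the same rise. Each definition is followed by the same sentence: "If the patient had a platelet transfusion during the period, the patient is considered as not assessable".

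SAP 2.8.3 sets the tables: "The following summary tables will be provided by cycle during induction and consolidation". They give the number of patients with thrombocytopenia, and "among them the duration of thrombocytopenia and the time between chemotherapy (cytarabine or daunorubicin) start and non-transfused recovery from thrombocytopenia". Protocol 10.5.3.1 presents safety tables by treatment arm.

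The neutropenia definitions in SAP 2.1.1 carry no such exclusion. The section closes by saying that further analyses "might be performed, if need be, in order to better characterize the influence of concomedications and blood transfusions" on recovery, without giving a method.

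**The concern.** Whether a patient is assessable depends on something that happens after randomization and is linked to the quantity measured. Platelets are transfused because the count is low, and each further day below the threshold is another chance of transfusion. If one arm has longer thrombocytopenia, more of its patients drop out of its own duration table.

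The rule also works against the endpoint it serves. A patient transfused at the nadir can later recover without support, and that recovery is discarded. A transfusion given after recovery, but within the same period, has the same effect.

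Patients with no count above the threshold in the period have no end date, and SAP 2.1.1 gives no censoring rule for them. SAP 2.8.1.1 does give one for time to first adverse event of special interest.

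At stake is a safety question the study could inform. Protocol 1.2.1.2 reports that midostaurin did not lengthen recovery in the earlier phase III trial, and Protocol 2.1 notes that there is little experience of midostaurin with the JALSG regimen. A table of never-transfused patients is a weak check on whether that reassurance carries over.

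**Working it through.** The plan states no expected assessable number for these tables, so there is no figure to reproduce.

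**Inputs from the documents**
- 62 patients randomized (SAP 2.1), allocation 1:1 (Protocol 6.5.2). Upper bound per arm: 62 / 2 = 31. Actual arm sizes are not given.
- Each table is restricted to patients with thrombocytopenia in that cycle (SAP 2.8.3). Only patients without complete remission (CR) receive a second induction, and only those in CR enter consolidation (Protocol 4.1.2.2). Denominators after the first induction are therefore smaller.
- Transfusion is at the investigator's discretion (Protocol 6.4.1). No platelet trigger or transfusion rate is stated.

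**Step 1: how many remain.** With an assumed transfused proportion t among patients in the table, the expected number assessable is at most 31 x (1 - t). The probabilities are binomial with n = 31.

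| Assumed t | Expected assessable per arm | Chance of 3 or fewer |
|---|---|---|
| 50% | 15.5 | about 0 |
| 70% | 9.3 | 0.7% |
| 80% | 6.2 | 11% |
| 90% | 3.1 | 62% |
| 95% | 1.6 | 93% |

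At 95% the chance that an arm has nobody assessable is 0.95^31 = 20%.

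**Step 2: direction of the bias.** Illustrative simulation, all inputs assumed: lognormal durations with medians of 10 and 13 days, log-SD 0.4 or 0.6, and a constant daily chance of transfusion while platelets are low. Here t is the proportion transfused in the 10-day arm. The true difference in medians is 13.0 - 10.0 = 3.0 days.

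| t | log-SD | Medians among assessable (days) | Apparent difference (days) |
|---|---|---|---|
| 50% | 0.4 | 9.0 and 11.4 | 2.4 |
| 50% | 0.6 | 8.1 and 10.0 | 1.9 |
| 90% | 0.4 | 7.3 and 8.9 | 1.6 |
| 90% | 0.6 | 5.5 and 6.4 | 0.9 |

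The 13-day arm loses more patients: 58-59% when the other loses 50%, and 94% when the other loses 90%. Both medians fall and the difference shrinks, even at a moderate transfusion rate.

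**Step 3: do other outputs fill the gap?** SAP 2.8.3 keeps transfused patients in the thrombocytopenia incidence, the number and percentage needing platelet transfusion, the worst-grade shift tables and the listings. These show occurrence, worst grade or raw data. None summarises duration or recovery time in transfused patients.

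**The case against.** The rule has a sound purpose. A count lifted above 20 x 10^9/L by transfusion is not marrow recovery, and the endpoint is explicitly transfusion-free. The lack of a matching exclusion for neutropenia fits that purpose. An arm transfused more often would show it in the adjacent transfusion table. The tables are descriptive, with no test or between-arm estimate.

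All of this stands. It limits the consequence and justifies not counting a rise caused by transfusion. It does not justify discarding the patient, since a look-back window serves the same aim. Nor do the other tables give recovery times for those removed.

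A reader might go further and infer that the table will be nearly empty. That needs roughly 90% or more transfused, a rate the documents neither state nor exclude. The earlier trial's report of severe myelosuppression in nearly all patients (Protocol 1.2.1.2) is not a transfusion rate. A reader might also infer that only the mildest cases remain. With discretionary transfusion and no stated trigger, the supportable statement is that longer or deeper cases are preferentially removed.

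**Conclusion.** The exclusion makes the by-cycle duration and recovery summaries conditional on a post-randomization event plausibly tied to the outcome, and unrecovered patients are not provided for. The likely effect is to understate durations and any difference between arms. This rests on one assumption: that transfusion is likelier with longer or deeper thrombocytopenia.

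The number lost cannot be derived from the documents. The range of about 15.5 down to 1.6 assessable per arm applies assumed rates of 50% to 95% to an upper bound of 31. It is not an estimate for any particular cycle.

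The impact is confined to two descriptive secondary safety measures; EFS and the success criterion are untouched. The only remedy now in the plan is optional and has no stated method, so this is a low-cost improvement worth making.

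**What to change.** 1. Keep the present table, and show the numbers assessable and not assessable beside each summary, by arm and cycle.
2. Add an analysis that retains transfused patients. Define recovery as the first count above 20 x 10^9/L with no platelet transfusion within a look-back window stated in advance. Estimate time from chemotherapy start by cumulative incidence, in all patients with thrombocytopenia in that cycle.
3. Treat death, and start of the next cycle without recovery, as competing events, and censor at the last count. Simple censoring at death or next-cycle start would not do: death precludes recovery, and a second induction is given because CR was not reached, so that censoring would be informative.
4. Define the period. SAP 2.1.1 refers to a period for platelets and a phase for neutrophil recovery, while SAP 2.8.3 tabulates by cycle.

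The cost is SAP wording, one derivation and one table. No new data should be needed: transfusions are recorded (Protocol 6.4.1) and listed (SAP 2.8.3), and the existing rule already needs their timing. The drawback is that the clinical team must choose a look-back window. This SAP is dated 06-Dec-2022, after the unblinding planned at the primary analysis (cut-off 30 November 2020), so the analysis should be labelled as added after the primary analysis.

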## **2.2 Analysis sets**

### **Full Analysis Set**

The Full Analysis Set (FAS) comprises all patients to whom study drug (midostaurin/placebo) has been assigned by randomization. Therefore, all Japanese patients treated during the part 1 will not be eligible for the FAS. According to the intent to treat principle, patients will be analyzed according to the treatment and strata they have been assigned to during the randomization procedure.

### **Per protocol set (PPS)**

The Per-Protocol Set (PPS) consists of a subset of the patients in the FAS who are compliant with requirements of the study protocol.

Oncology standards for protocol deviations **potentially** leading to exclusion from the PPS are:

- type of indication different from those required by the CTP (e.g., incorrect histology/cytology, not refractory, not metastatic, different grade of cancer, etc.)
- if prior therapy does not match with CTP requirements in terms of number and types of previous therapy regimens

- missing or incomplete documentation of stage of disease (as required in the CTP)
- another anti-neoplastic therapy administered after start of study treatment and prior to first efficacy assessment
- study treatment received different from treatment assigned by randomization

### **Safety set**

The Safety Set includes all randomized patients who received at least one dose of study drug. Patients will be analyzed according to the part in which they are enrolled and the study treatment received, where treatment received is defined as the randomized treatment if the patient took at least one dose of that treatment or the first treatment received if the randomized treatment was never received.

### **Other**

#### **Pharmacokinetic analysis set for all (PAS-all)**

The Pharmacokinetic analysis set for all (PAS-all) includes all patients who took at least one dose of midostaurin and provide at least one evaluable PK concentration.

For a concentration to be evaluable, patients are required to:

- Take the planned dose of midostaurin prior to sampling
- For pre-dose samples: do not vomit within 4 hours after the dosing of midostaurin prior to sampling, have the sample collected before the next dose administration
- For post-dose samples: do not vomit within 4 hours after the dosing of midostaurin

The PAS-all will be the primary population used for all pharmacokinetic analyses using trough concentration data.

#### **Pharmacokinetic analysis set for full PK (PAS-full)**

The Pharmacokinetic analysis set for full PK (PAS-full) includes all patients in the PAS-all, who provide an evaluable PK profile. A profile is considered evaluable if all of the following conditions are satisfied:

- Patient receives the planned dose of midostaurin on C1D8 of induction therapy
- Patient does not vomit within 4 hours of the dosing of midostaurin on C1D8 of induction therapy
- Patient provides at least one primary PK parameter

The PAS-full will be the primary population used for all pharmacokinetic analyses using full PK data.

### **Patient Classification:**

Patients may be excluded from the analysis populations defined above based on the protocol deviations entered in the database and/or on specific subject classification rules defined in [Table 2-2](#).

**Table 2-2      Subject classification based on protocol deviations and non-PD criteria**

Analysis set	PD Identifier leading to exclusion (Edit Check Specifications V9.0)	Non protocol deviation leading to exclusion
FAS	INCL06	Not applicable
Safety set	INCL06	No dose of study drug
Per-protocol set	INCL01A, INCL01A01, INCL01A02, INCL01B, INCL04, INCL06, EXCL05, EXCL06, EXCL07, EXCL08, EXCL09, COMD01, TRT03, TRT07, TRT10, OTHER02, OTHER04, OTHER11, COMD03	Patient randomized with confirming FLT3 is wild-type or undeterminate
PK Analysis Set	INCL06, EXCL07	See definition of PK analysis set
Full PK Analysis Set	INCL06, EXCL07	See definition of full PK analysis set

### **Withdrawal of Informed Consent**

Any data collected in the clinical database after a subject withdraws informed consent from all further participation in the trial, will not be included in the analysis. The date on which a patient withdraws full consent is recorded in the eCRF.

#### **2.2.1      Subgroup of interest**

##### **Efficacy**

The EFS and OS will be summarized by the following subgroups to examine the homogeneity of treatment effect across demographic and baseline disease characteristics will be performed:

- FLT3 mutation status (stratification factor: ITD allelic ratio <0.7, ITD allelic ratio ≥ 0.7, TKD)
- chemotherapy regimen (stratification factor: RATIFY regimen, JALSG regimen)
- gender
- age category: < 60 years, ≥ 60 years

For each of subgroups, the treatment effect will be assessed separately within each category. The HR and their 95% CIs will be presented by means of forest plots. Unstratified analysis will be performed for each of the subgroups.

The CR rate will also be summarized by the subgroup shown above. The difference of CR rate between treatments and their 95% CIs will be presented by means of forest plot.

##### **Safety**

AEs, regardless of study treatment relationship, will be summarize by the following subgroups:

- age category: < 60 years, ≥ 60 years
- chemotherapy regimen (stratification factor: RATIFY regimen, JALSG regimen)

- strong CYP3A4 inhibitor intake (Yes/No), for patients who received/did not receive strong CYP3A4 inhibitor (listed in protocol appendix 2) concomitant treatments during the study.

For each subgroup, AEs regardless of study treatment relationship will be summarized by SOC, PT and maximum CTC grade, and by phase.

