In this study, the safety profile for both the midostaurin and placebo groups was relatively consistent. Most AEs, AEs suspected to be related to study drug, SAEs and AEs leading to discontinuation occurred at similar frequencies in both midostaurin and placebo control groups. The most frequent adverse events reported in the combination setting were predominantly cytopenias (thrombocytopenia, anemia, neutropenia) and gastrointestinal events (nausea, vomiting) compared to those for patients receiving midostaurin monotherapy, as expected from the known toxicities of the RATIFY regimen.

As expected, the most frequent grade 3/4 AEs in both groups were related to myelosuppression (neutropenia, anemia, thrombocytopenia, febrile neutropenia) and occurred in nearly all patients during the induction/consolidation phases. Midostaurin did not increase the incidence or severity of cytopenias (leukopenia, neutropenia, thrombocytopenia) febrile neutropenia, infections or bleeding events and did not negatively impact time to recovery, suggesting that adding midostaurin to chemotherapy does not increase the risk for such events. Cytopenias are common findings in patients with AML who are treated with chemotherapy ([Atallah et al 2007](#)).

The most frequent non-hematologic grade 3/4 AEs in the midostaurin group were infections (device-related), diarrhea, and exfoliative dermatitis; for the placebo group, the most common were hypokalemia, diarrhea, and pneumonia. AEs were generally balanced between the two treatment arms, with the exception of exfoliative dermatitis and transaminase elevations, which occurred more frequently in midostaurin-treated patients.

Non-fatal cases of cardiac dysfunction, including congestive heart failure, occurred in a small proportion of patients (1.3% in both treatment groups). In the advanced SM population, 7.0% had cardiac dysfunction, and a few patients had notably decreased LVEF (<45%).

Pulmonary toxicity/ILD events (primarily pneumonitis) occurred in approximately 14% of patients in Study [\[A2301\]](#), with a similar frequency in the midostaurin (including one fatal case) and placebo groups. In the advanced SM population, ILD AEs were reported in 3.5% of patients, none of which had a fatal outcome.

Clinical data indicate that strong CYP3A4 inhibitors increase midostaurin steady-state exposure 2.7 fold, with limited impact on the two major metabolites. In Study [\[A2301\]](#), concomitant

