### **1.1.2.2 Treatment phase**

#### **Induction therapy**

All screened patients will start induction therapy with chemotherapy (daunorubicin and cytarabine) from Day 1 to Day 7, while the FLT3 mutation is being determined.

An Interactive Response Technology (IRT) system will be used to randomize patients to the study treatment groups and the patient eligibility checklist will be embedded into the IRT randomization process.

Only randomized patients (with FLT3 mutation) will receive midostaurin/placebo, orally twice a day, on days 8 to 21.

Patients who achieve CR already with induction cycle 1 will go directly to consolidation therapy without a second cycle of induction therapy. Patients who do not achieve CR with one cycle of induction will receive a second induction cycle with same treatment than in cycle 1.

Patients not achieving CR after induction 2 will discontinue study treatment and will be followed in safety follow-up and survival follow-up.

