## **On-treatment assessment/event and observation periods**

For all safety analyses, the overall observation period will be divided into three mutually exclusive segments:

1. **pre-treatment period:** from day of patient’s informed consent to the day before first dose of study treatment

2. **on-treatment period:** from day of first dose of study treatment to 30 days after last dose of study treatment
3. **post-treatment period:** starting at day 31 after last dose of study treatment.

Safety summaries (tables, figures) include only data from the on-treatment period with the exception of baseline data which will also be summarized where appropriate (e.g., change from baseline summaries). In addition, a separate summary for death including on treatment and post treatment deaths will be provided. In particular, summary tables for adverse events (AEs) will summarize only on-treatment events, with a start date during the on-treatment period (**treatment-emergent** AEs).

However, all safety data (including those from the post-treatment period) will be listed and those collected during the pre-treatment and post-treatment period will be flagged.

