##### **Concomitant medications**

Concomitant therapy is defined as all interventions (therapeutic treatments and procedures) other than the study treatment administered to a patient coinciding with the study treatment period. Concomitant therapy include medications (other than study drugs) starting on or after the start date of study treatment or medications starting prior to the start date of study treatment and continuing after the start date of study treatment.

Concomitant medications will be coded using the WHO-DD and summarized by ATC class and preferred term using frequency counts and percentages. The same analyses will be performed for strong CYP3A4 inhibitors. Surgical and medical procedures will be coded using MedDRA and summarized by SOC and preferred term. These summaries will include:

1. Medications starting on or after the start of study treatment but no later than 30 days after start of last dose of study treatment, and
2. Medications starting prior to start of study treatment and continuing after the start of study treatment.

All prior and concomitant therapies will be listed. Any concomitant therapies starting and ending prior to the start of study treatment or starting more than 30 days after the last date of study treatment will be flagged in the listing. The safety set will be used for all concomitant medication tables and listings.

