## 2.8.1 Adverse events (AEs)

Summary tables for adverse events (AEs) will include only AEs that started or worsened during the on-treatment period, the treatment-emergent AEs.

Adverse events are coded using the Medical dictionary for regulatory activities (MedDRA) terminology.

AEs will be assessed according to the Common Terminology Criteria for Adverse Events (CTCAE) version 5.0. The CTCAE represents a comprehensive grading system for reporting the acute and late effects of cancer treatments. CTCAE grading is by definition a 5-point scale generally corresponding to mild, moderate, severe, life threatening, and death. This grading system inherently places a value on the importance of an event, although there is not necessarily proportionality among grades (a grade 2 is not necessarily twice as bad as a grade 1).

AEs will be summarized by number and percentage of subjects having at least one AE in each primary system organ class (SOC) and for each preferred term (PT) using MedDRA coding. A subject with multiple occurrences of an AE will be counted only once in the respective AE category. A subject with multiple CTCAE grades for the same preferred term will be summarized under the maximum CTCAE grade recorded for the event. AE with missing CTCAE grade will be included in the 'All grades' column of the summary tables.

In AE summaries, the primary system organ class will be presented alphabetically and the preferred terms will be sorted within primary SOC in descending frequency. The sort order for the preferred term will be based on their frequency in the investigational arm

In AE summaries by phase, AEs newly recorded between the start date and the end date of the phase will be used, that is, AEs continued from the previous phases and not newly recorded will not be included in the summary. If a subject discontinued study treatment in a specific treatment phase, then all AEs observed within 30 days from the study treatment discontinuation in addition to those observed during this treatment phase will be considered.

The following AE summaries will be produced by phase and treatment group;

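### The AE subgroup by strong CYP3A4 inhibitor use (SAP 2.2.1) rests on a post-baseline ever/never flag with no time ordering, so its user/non-user comparison is confounded in a direction the documents do not fix

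*SAP*

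**What the plan says.** SAP 2.2.1 (Safety) lists three AE subgroups: age, chemotherapy regimen, and a Yes/No split by receipt of a "strong CYP3A4 inhibitor (listed in protocol appendix 2) concomitant treatments during the study". It adds: "For each subgroup, AEs regardless of study treatment relationship will be summarized by SOC, PT and maximum CTC grade, and by phase". It sets no date, landmark or overlap condition.

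The AEs counted are defined in SAP 2.8.1: "Summary tables for adverse events (AEs) will include only AEs that started or worsened during the on-treatment period, the treatment-emergent AEs". SAP 2.1.1 sets that period as "from day of first dose of study treatment to 30 days after last dose of study treatment". Study treatment includes the chemotherapy, so counting begins on Day 1. The study drug starts a week later: "Only randomized patients (with FLT3 mutation) will receive midostaurin/placebo, orally twice a day, on days 8 to 21".

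The nearest thing to a window for the inhibitor is in SAP 2.4.2.2, whose concomitant-medication tables (repeated for strong CYP3A4 inhibitors) include "Medications starting on or after the start of study treatment but no later than 30 days after start of last dose of study treatment". The by-phase rule in SAP 2.8.1 assigns each newly recorded AE to a phase. It does not assign inhibitor use to a phase.

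Protocol 10.5.3.5 describes the safety subgroups as demographic and baseline disease characteristics. Age and regimen fit that description; inhibitor use after entry does not.

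**The concern.** A patient must remain under observation long enough to start an inhibitor. The same extra time gives more opportunity for an AE, so ever-users can show more AEs than never-users without any interaction. Causation can also run backwards, since an infection may be the reason an azole is given. For an AE that ends treatment or life the logic turns round: the event removes the chance of becoming a user.

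The interaction is worth describing properly. Protocol 1.2.1.2 states: "Clinical data indicate that strong CYP3A4 inhibitors increase midostaurin steady-state exposure 2.7 fold". The SAP plans no other AE table by inhibitor use. As defined, this table could suggest an interaction for some AEs and obscure one for others.

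**Working it through.** **What follows from the text alone.** Take a patient with an AE on Day 5, study drug from Day 8, and a strong inhibitor given only in consolidation. The AE is treatment-emergent and falls in induction, and the patient is flagged *Yes*. It is therefore tabulated as an induction AE in an inhibitor user, although neither the inhibitor nor midostaurin/placebo had been given. A patient whose inhibitor began after the last study-drug dose is not excluded from *Yes* either.

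**Size.** The plan gives no figure for this subgroup, so there is nothing to reproduce. Inputs from the documents: 62 randomised, about 31 per arm (Protocol, Amendment 3); in A2301, median exposure of 42.0 days on midostaurin (range 2-576) and 34.0 on placebo, and 45% of patients given a moderate or strong inhibitor (Protocol 1.2.1.2). All rates below are assumptions, and no scenario contains an interaction.

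*Closed form, all phases pooled.* Let time on treatment, first AE and inhibitor start be independent exponentials with rates 1, a and b (the time unit cancels). Assume 30% have the AE and 45% become users:
- a = 0.30/0.70 = 0.429; b = 0.45/0.55 = 0.818; 1 + a + b = 2.247
- P(AE and user) = 0.30 + 0.45 - 1 + 1/2.247 = 0.195
- AE risk in users = 0.195/0.45 = 43.4%; in non-users = (0.30 - 0.195)/0.55 = 19.1%; ratio 2.3
- P(AE first, then inhibitor, both on treatment) = 0.45 - 0.818/2.247 = 0.086; share of users' first AEs that precede the inhibitor = 0.086/0.195 = 44%

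*Simulation, all phases pooled* (400,000 patients per setting, treatment capped at 18 months):

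| Pattern of inhibitor use | Users | Non-users |
|---|---|---|
| Starts spread over time (median treatment 4 months, 45% users, 30% with AE) | 42.9% | 19.5% |
| Random, all from Day 1 | 30.0% | 30.0% |
| AE triggers the inhibitor in 25% of AE patients | 47.2% | 15.9% |
| AE triggers the inhibitor in 50% of AE patients | 52.2% | 11.8% |
| Treatment-ending AE, constant hazard | 44.4% | 46.3% |
| Treatment-ending AE, hazard falls after induction | 19.4% | 32.0% |

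The first row was repeated over 18 settings (median treatment 2, 4 or 6 months; 30, 45 or 60% users; 10 or 30% with the AE). The risk ratio ran from 1.8 to 3.3, and 31-50% of users' first AEs preceded the inhibitor. For treatment-ending AEs the pooled table is close to neutral at constant hazard; the clear reversal needs a hazard that declines.

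*By phase, as the SAP tabulates.* For an induction table (1.5 months assumed) and an AE that does not end treatment, with hazard 0.2/month, users had 25.5% and non-users 20.9%; 82% of the users' induction AEs preceded the inhibitor. At a lower AE rate (0.08/month, mean treatment 5 months, 10-30% on an inhibitor at start, later starts 0.05-0.2/month), the pooled table gave 36-41% against 20-27%. The same assumptions limited to induction gave 10.3-10.8% against 8.5-9.5%. For a treatment-ending AE the induction table gave about 3% against 21%. Consolidation and continuation tables were not simulated.

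*Placebo as control.* With 31 per arm, AE hazard 0.06/month and 45% users, the user-minus-non-user difference within an arm averaged +0.21 (SD 0.16) and was positive in 90% of trials. The midostaurin-minus-placebo contrast of that difference averaged 0.00, with SD 0.23. A 95% range is thus about ±1.96 × 0.23 = ±0.45.

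*With time order restored.* In the same 18 settings, the first-AE rate per person-time after versus before inhibitor start had a ratio of 0.985 to 1.015, as it should with no interaction.

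**The case against.** A reader might infer that the table will show more toxicity in users even with no interaction. The documents do not support that. Protocol 1.2.1.2 describes inhibitor use in A2301 as mainly antifungal prophylaxis during induction and consolidation, and Protocol 6.4.1 permits prophylactic antifungals here. If use is effectively from Day 1 and unrelated to risk, there is no bias. The same section reports no clinically relevant difference in grade 3-4 AEs by inhibitor use in A2301, though without saying how use was timed. Inhibitor start dates in this trial are not given.

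A reader might also infer that this is the only planned analysis bearing on the interaction. It is not. SAP 2.10 models drug-related AESIs, and AEs leading to discontinuation, on the last trough before onset. That is time-ordered and works through exposure, the route by which an inhibitor would act. It may be dropped when AESI events are few (fewer than 10 is the example given), and it does not tabulate by inhibitor use. The 2.7-fold figure also needs context: the protocol adds that the two major metabolites are little affected, and reports a 1.44-fold increase in A2301, where moderate inhibitors were included.

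The tables are shown by arm, and placebo patients share the artefact. That is a real control when both arms have similar time on treatment and inhibitor use, but it is imprecise at this sample size and the SAP does not specify the contrast.

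All of this limits the size and certainty of the bias. None of it puts the AE and the inhibitor in order in this table.

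**Conclusion.** The definition is defective in time order, and that follows from the SAP text without any assumption. AEs before the inhibitor, before Day 8, or in a different phase from the inhibitor are tabulated under users, and no other rule corrects this table.

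The consequence is conditional. The comparison leans toward more AEs in users when starts are spread over time or triggered by AEs. It leans toward fewer for fatal or treatment-ending AEs, notably in the induction table, and is near neutral for prophylaxis from Day 1. Ratios of 1.8 to 3.3 apply only to pooled phases with starts spread over time under assumed rates; the simulated induction gaps for AEs that do not end treatment were smaller. Neither the sign nor the size for this trial can be derived from the documents.

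The table is descriptive and carries no test or success criterion, and the protocol makes safety subgroups optional. This is an inexpensive improvement of modest priority.

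**What to change.** Replace the ever/never flag in SAP 2.2.1 with one of two date-based rules.

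1. **Overlap (preferred).** Within each phase and arm, count AEs with onset while a strong inhibitor and midostaurin/placebo overlap. Give exposure-adjusted incidence for overlap and for non-overlap study-drug time. State whether a lag after the last dose of either drug counts as overlap, because study drug is given only on Days 8-21 of induction and consolidation cycles.
2. **Landmark.** Within each phase, flag inhibitor use that is ongoing at the first study-drug dose of that phase, and count only AEs with onset on or after that dose. Requiring use to be ongoing stops an inhibitor that ended in an earlier phase from counting as current; the onset rule removes Day 1-7 AEs.

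Add a footnote that any user/non-user gap on midostaurin is to be read against the same gap on placebo.

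The cost is a wording change, a derived flag from AE, concomitant-medication and dosing dates already recorded, slightly more programming, and smaller cells. Under the landmark rule, patients who start an inhibitor later in the phase are classed as *No*. Neither rule removes confounding by the reason for prescribing, since inhibitor use remains the investigator's choice.
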